6.2.4. Sample size

Using the GRANMO sample matingc, Version 7.12 was calculated for the difference of media coupled in energy expenditure at rest of the combination of passive and active external (in two methods, by thermal plate and convective air blanket) versus passive external heating.

Accepting an alpha risk of 0.05 and a beta risk of 0.2 in a bilateral contrast, 34 subjects are required to detect a difference equal to or greater than 0.15 units. A standard deviation of 0.3 is assumed. A 5% tracking loss rate has been estimated.

The difference expected to be found in the resting metabolic expenditure rate of at least 0.1 times the GMB. The increase in baseline metabolic expenditure of these patients in studies with burned patients was 1.4 times with standard deviation of 0.2 - 0.32 times. The sample will be adjusted to the standard deviation values presented in the pilot sample.

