6.3.1. Dependent variables

At the stage of defining thermal comfort, the variables shall be collected:

- Operating temperature (Dry temperature + radiant temperature)
- Relative humidity
- Air speed

For the assessment of nutritional data and energy expenditure, the variables will be collected: Weight, Height, Ideal Weight, BMI (kg/m²), FiO₂, Charlson Index, Nutri- Score, Nutritional Biochemistry, Serum Albumin (g/dl). The calculation of theoretical caloric requirements (kcal/day) using the Penn State predictive formula and the protein requirements/day (gr/day) calculation will be included.

- Metabolic expenditure, calculated by Indirect calorimetry collecting the variables:
 - VCO₂: Carbon dioxide production (Avg VCO₂, VCO₂ hp)
 - VO₂: Consumption of O₂ (Avg VO₂, VO₂ HP)
 - o RQ: Cociente respiratorio (Avg RQ, Avg EE)
 - EE: Energy expenditure in kcal/d (Avg EE/m², AVG EE/Kg)
- Body temperature via surface thermometer
- Central temperature recorded by bladder probethermometer, from entry and registration c/8h until 7 days after admission. Time recording of temperature during heating analysis.
- Calculation of liquid loss estimation.

The difference of the metabolic state at rest versus the actual one will be categorized by qualitative scale.

Due to the critical condition of the patient, the CONFORT scale will be collected for the evaluation of sedation and pain in the critical patient.

For the assessment of the comfort status (NOC 2008) and thermoregulation (NOC 0800) according to Thert scale will be carried out in the application of the two heating techniques.

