6.5. Data analysis

The values of the temperatures measured in the empirical study, the discrete and absolute variables according to descriptive in ranges, maximum and minimum, trend, mean and median valuesshall berecorded.. The VMP and PPI values willbe calculated through the software associated with the Testo® measuring instruments.

A descriptive analysis of the variables obtained shall be carried out. Continuous quantitative variables shall be analysed by the Kolmodorov-Smirnov test and described as mean standard deviation (DS) in case of normal distribution, or as median and range if the distribution does not follow the normal distribution. Qualitative variables shall be described by absolute and relative frequencies. A single-rate analysis shall be performed by observing as variables main dependent temperature and metabolic expenditure. With a 95% confidence interval (p<0.05) quantitative variable means will be contrasted using Student t or Mann-Whitney's U-depending on the sample distribution. The Chi-square test for contingency tables and the Fisher test will be used to assess association of qualitative variables.

A logistic regression model may be established based on the results, analyzing the strength of association in explanatory and predictive terms.

IBM SPSS Stadisticssoftware® v.23 will be used for statistical data analysis

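### The only regression named is an optional, results-driven logistic model with no stated outcome, while both main outcomes are continuous, repeated within patient, and given no paired or repeated-measures analysis

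*Combined protocol and SAP*

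**What the plan says.** Section 6.5 takes temperature and metabolic expenditure as the main dependent variables and compares means by Student t or Mann-Whitney U, according to distribution. It does not say that the t test is paired. For categorical data it adds: "The Chi-square test for contingency tables and the Fisher test will be used to assess association of qualitative variables". The only regression follows: "A logistic regression model may be established based on the results, analyzing the strength of association in explanatory and predictive terms". No linear, mixed or repeated-measures model appears.

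Section 6.3.1 records energy expenditure in kcal/day, and also states: "The difference of the metabolic state at rest versus the actual one will be categorized by qualitative scale". The categories are not defined.

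Section 6.4.2 applies the three heating methods to each patient on three consecutive nights in a fixed order: ambient temperature alone, then with the thermal plate, then with the blanket.

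Section 6.2.4 sizes the trial for a paired contrast, the "difference of media coupled in energy expenditure at rest", and finds that "34 subjects are required to detect a difference equal to or greater than 0.15 units".

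**The concern.** The analysis named does not match the design. The sample size depends on each patient serving as his or her own control, but section 6.5 contains nothing that clearly uses the pairing. Mann-Whitney, chi-square, Fisher and ordinary logistic regression all assume independent observations.

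The one model meant to explain and predict needs a categorical outcome, and neither main outcome is categorical as measured. Section 6.3.1 already plans to categorise a metabolic difference, so a split of expenditure is a natural route into the logistic model. Because the model is to be set up in the light of the results, its outcome, cut-point and predictors could all be chosen after the data are seen. At stake are the information lost by categorising, the pairing on which 34 patients depends, and the credibility of any explanatory claim.

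**Working it through.** **Step 1. Reproduce the sample size.** Inputs from section 6.2.4: "Accepting an alpha risk of 0.05 and a beta risk of 0.2 in a bilateral contrast"; difference 0.15; "A standard deviation of 0.3 is assumed"; "A 5% tracking loss rate has been estimated".

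For paired means, n = ((1.960 + 0.842) × 0.3 / 0.15)² = 31.4, so 32 evaluable. Allowing for loss, 32 / 0.95 = 33.7, so 34. The stated figure reproduces exactly if 0.3 is the SD of the within-patient difference.

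**Step 2. Power of the continuous paired analysis, 32 evaluable.** The standardised effect is 0.15 / 0.3 × √32 = 2.83. The normal approximation gives Φ(2.83 − 1.96) = 80.7%; the paired t test gives 78.2%. Half of the latter is about 39%.

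**Step 3. Assumptions for a split outcome.** The documents give neither a cut-point nor a within-patient correlation. I take:
- mean 1.4 times basal (section 6.2.4), falling by 0.15 to 1.25;
- single-night SD s of 0.2 to 0.32 (the range that section 6.2.4 quotes from studies in burned patients);
- SD of differences held at 0.3, so the correlation is ρ = 1 − 0.3² / (2s²), which runs from −0.13 at s = 0.2 to 0.56 at s = 0.32;
- cut-points 1.2, 1.325 (midway between the means), 1.4 and 1.5.

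**Step 4. One case in full: s = 0.3, ρ = 0.5, cut 1.4.** The proportion above the cut is 0.500 under passive heating and 1 − Φ(0.15 / 0.3) = 0.309 with active heating. Under the bivariate normal, the two discordant probabilities are 0.273 and 0.082, with sum ψ = 0.355 and difference d = 0.191. Asymptotic McNemar power is Φ((d√32 − 1.96√ψ) / √(ψ − d²)) = Φ(−0.15) = 44%. Enumerating the same test gives 43%, and the exact McNemar test 34%. A Wald test from unpaired logistic regression gives about 33% by simulation. Separate simulation runs put the three tests at about 42%, 33% and 32%, so differences of a point or so are simulation error.

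**Step 5. Range over the four cut-points.** McNemar figures are enumerated or simulated. Logistic figures are from 40,000 simulated trials per SD. The unpaired t column uses no split and is Φ(0.15 / (s√(2/32)) − 1.96).

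| s | ρ | Exact McNemar | Asymptotic McNemar | Unpaired logistic | Unpaired t, no split |
|---|---|---|---|---|---|
| 0.20 | −0.13 | 38–53% | 47–62% | 46–68% | 85% |
| 0.25 | 0.28 | 33–43% | 43–52% | 37–51% | 67% |
| 0.30 | 0.50 | 29–35% | 39–45% | 27–36% | 52% |
| 0.32 | 0.56 | 27–33% | 37–42% | 23–31% | 47% |

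**Step 6. Separate the two losses.** At s = 0.3 and cut 1.4, ignoring the pairing alone takes power from 78% to about 52%, a loss of 26 points. Splitting the outcome then takes it from 52% to about 33%, a further 19. At s = 0.2 the implied correlation is negative and ignoring the pairing costs nothing, so the mildest figures belong to a case that is unlikely for one patient on consecutive nights.

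**The case against.** The strongest answer is that nothing in the plan splits expenditure for the comparison of heating methods. Section 6.5 compares means, section 6.2.4 is sized on a mean difference, and the logistic sentence is permissive. The qualitative scale in section 6.3.1 concerns resting against actual metabolic state; it is not said to be binary or to be the logistic outcome. Section 6.3 also collects early and hospital mortality, for which logistic regression would be natural. The chi-square and Fisher tests may be meant for patient-level variables such as sex or origin of the burn, where independence is not in doubt. All of this stands, and it means that the main analysis and its planned power do not depend on the logistic model.

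A reader might infer that the plan will lose more than half of its power through dichotomising. The documents do not support that. They commit to no split, and in step 5 the loss exceeds half only for some combinations of SD, cut-point and test: with asymptotic McNemar most cases stay at or above 39%. Where unpaired logistic regression falls well below that, part of the fall comes from discarding the pairing. Nor can the model be called multivariable, since no covariates are listed.

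The objection does not supply what is missing: a stated outcome for the only regression, and any analysis that uses the repeated nights.

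**Conclusion.** The point holds as a mismatch between design and analysis, together with an open-ended, results-driven model. It does not show that the primary contrast is underpowered by dichotomising. A change is worth making before the data are analysed, because the sample size relies on pairing that section 6.5 never clearly uses.

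The size is conditional. If expenditure were split, power would fall from about 78% to roughly 27–62% with a paired test, or 23–68% with unpaired logistic regression. Every case examined loses power. These figures rest on the assumed cut-points and correlations, on normality, and on the 0.15 difference that reproduces 34 patients. Confidence in the mismatch is high; confidence in any single power figure is low, because the documents fix neither cut-point nor correlation.

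**What to change.** In section 6.5:

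1. State that energy expenditure and temperature will be compared between heating methods on the continuous scale, by a prespecified linear mixed model with heating method as fixed effect and patient as random effect. This should govern the between-method comparison in place of the unqualified Student t or Mann-Whitney wording. A paired t test or repeated-measures analysis of variance would also respect the design.
2. Keep the qualitative scale of section 6.3.1 for description, and define its categories in advance.
3. Limit any logistic regression to patient-level binary outcomes such as mortality, name the outcome and predictors beforehand, and label it exploratory.

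The cost is wording only, with no extra patients or measurements. The mixed model uses all three nights but does not separate heating method from night, because every patient follows the same order; section 6.5 should acknowledge that limit.

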6.6 Ethical Aspects

Confidentiality and custody of the data collected in the investigation will be ensured by coding the participants. A code will be assigned to each participant in a separate file to the data collection that will only be accessed by the principal investigator.

MSN [name] Universitat Rovira i Virgili / Hospital Universitario Rio Hortega Valladolid /Sanidad Castilla y León /Universidad de Valladolid Optimal Heating Temperature in Major Burns Patients

Study Protocol, Statistical Analysis Plan (SAP), Informed Consent Form (ICF). Version 1.0

The research project is agreed with the principles of bioethics in biomedical research developed in the Helsinki Declaration ratified in Fortaleza (Brazil) in 2013 and the Oviedo Convention on the Protection of Human Rights and Dignity promoted by the Council of Europe and validated in

2000 in Spain.

The information provided to the participants ortheir representatives in compliance with the Biomedical Research Act 14/2007, of July 3,, will be provided through the patient information

sheet.

The processing of the data of the study, access, confidentiality and privacy regulated by: Organic Law 15/1999, of December 13, Protection of Personal Data, Law 41/2002 of 14 November, basic regulation of patient autonomy and rights and obligations in the field of information and clinical documentation and updating Regulation (EU) 2016/679 of the European Parliament and of the Council of 27 April 2016 on the protection of natural persons with regard to the processing of personal data and on the free movement of such data. The same, is declared compliance with regulations or regulations that may be ordered later at the beginning of the study.

In accordance with RD 223/2004, of February 6, the study will be evaluated by the Ethics Committee of Research with medicines of the health area Valladolid West assessing the methodology, ethical and legal aspect and balance of the risks and benefits in the realization of the study.

6.6.1 Statement of Interest

The Principal Investigator declares that he/she has no conflict of interest, no contractual relationship with the materials or products that are included in the study.

6.6.2 Informed information and consent sheet

An information sheet will be provided to participants (or representative if necessary), candidates for inclusion in the study informing about the content of the study, their participation and rights as reflected in *Annex III*..

Acceptance of participation in the study will be reflected in the informed consent signed by the participant or his/her representative under the conditions shown in *Annex IV*.
